10.3.2 Other Secondary Efficacy Analysis

The other secondary endpoints are as follows:

- Achievement of an sPGA of clear or almost clear at Week 44
- Achievement of sPGA of clear at Week 44

Other secondary endpoints will be analyzed for the ITT_B_RR Population.

10.3.3 Further Endpoint Analyses

The further endpoints are as follows:

- Achievement of PASI 50 at all visits collected
- Achievement of PASI 75 at all visits collected
- Achievement of PASI 90 at all visits collected
- Achievement of PASI 100 at all visits collected
- Time until the first achievement of PASI 50, PASI 75, PASI 90, PASI 100 and sPGA of clear or almost clear

- Time until loss of PASI 75, and sPGA of clear or almost clear
- Change and percent change from baseline in PASI at all visits collected
- Achievement of an sPGA of clear or almost clear at all visits collected
- Achievement of an sPGA of clear at all visits collected
- Change from baseline in DLQI at all visits collected
- Achievement of a DLQI score of 0 or 1 at all visits collected
- Achievement of a reduction of 5 or more points from baseline in DLQI score at all visits collected, among subjects with baseline DLQI ≥ 5
- Change from baseline in WLQ at all visits collected
- Change and percent change from baseline in Nail Psoriasis Severity Index (NAPSI) at all visits collected, in subjects with baseline NAPSI > 0
- Change and percent change from baseline in Palmoplantar Psoriasis Severity Index (PPASI) at all visits collected, in subjects with baseline PPASI > 0
- Change and percent change from baseline in Psoriasis Scalp Severity Index (PSSI) at all visits collected, in subjects with baseline PSSI > 0

10.4 Handling of Multiplicity

The statistical comparisons for the primary efficacy variables and the ranked secondary variables will be carried out in the hierarchical order. This means that statistically significant results (P value ≤ 0.05) for the comparison in the higher rank (primary, then ranked secondary variables) are necessary to initiate the testing of the next comparison in the lower rank. Since a step-down procedure is used, each comparison will be tested at a significance level of 0.05 and overall alpha level of 0.05 will be preserved.

10.5 Efficacy Subgroup Analysis

To evaluate the consistency of the efficacy over demographic and other baseline characteristics, summaries and analyses will be performed in the following subgroups for the primary efficacy endpoints in Part A and the primary efficacy endpoint in Part B.

- Age group (< 40 years, $\geq 40 - < 65$ years, ≥ 65 years);

- Sex (male, female);
- Race (white, non-white);
- Smoking (current, ex or never)
- BMI (normal: < 25, over weight: $\geq 25 - < 30$, obese: ≥ 30);
- Region (US, Asia, Other)
- Baseline PASI score (by median);
- Baseline sPGA (3, 4)
- Psoriatic arthritis (yes [diagnosed or suspected], no)
- Ps Therapy History (Phototherapy or Photochemotherapy, TNF Antagonist, Other biologics, Non-biologic systemic therapy, All biologics, Naïve to all)

11.0 Safety Analysis

11.1 General Considerations

Safety analyses will include adverse events, laboratory, local tolerability, ECG, and vital sign measurements. Safety summaries will be provided using the safety population in each period as defined in Section 5.1. Comparison between risankizumab group and adalimumab group will be performed in the Safety Population in Safety_A and Safety_B_RR populations. Continuous variables will be analyzed using one-way ANOVA and categorical variables will be analyzed using Fisher's exact test. For the analyses of AEs, only P values ≤ 0.100 when rounded to three digits will be presented.

Missing safety data will not be imputed.

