5.3 ASSESSMENT OF SAFETY

Safety will be assessed descriptively based on:

- Adverse events
- Serious adverse events
- Clinical laboratory values (haematology, clinical chemistry and urinalysis)
- Intensity of adverse events assessed by Rheumatology Common Toxicity Criteria (RCTC) version 2.0 (refer to ISF for details).
- Physical examination
- Vital signs
- 12-lead ECG
- Local tolerability

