7.3.4 Safety analyses

Adverse events will be coded using the Medical Dictionary for Regulatory Activities (MedDRA) coding dictionary. Standard AbbVie summary tables and listings will be produced. All adverse events with an onset between start of treatment and end of the residual effect period (REP), a period of 15 weeks after the last administration of BI 655066 (active or placebo), will be assigned to the treatment period for evaluation.

All treated patients will be included in the safety analysis. In general, safety analyses will be descriptive in nature and will be based on AbbVie standards. No hypothesis testing is planned.

Statistical analysis and reporting of adverse events will concentrate on treatment-emergent adverse events. To this end, all adverse events occurring between start of treatment and end of the residual effect period will be considered 'treatment-emergent'. The residual effect period is defined as 15 weeks. Adverse events that start before first drug intake and deteriorate under treatment will also be considered as 'treatment-emergent'.

Frequency, severity, and causal relationship of adverse events will be tabulated by system organ class and preferred term after coding according to the current version of the Medical Dictionary for Drug Regulatory Activities (MedDRA).

Laboratory data will be analysed both quantitatively as well as qualitatively. The latter will be done via comparison of laboratory data to their reference ranges. Values outside the reference range as well as values defined as clinically relevant will be highlighted in the listings. Treatment groups will be compared descriptively with regard to distribution parameters as well as with regard to frequency and percentage of patients with abnormal values or clinically relevant abnormal values.

Vital signs, physical examinations, or other safety-relevant data observed at screening, baseline, during the course of the trial and at the end-of-trial evaluation will be assessed with regard to possible changes compared to findings before start of treatment.

More information about the safety analysis will be provided in the TSAP.

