4.3 Sample Size

This study is designed to show a benefit of risankizumab over adalimumab in terms of PASI 90 response and static Physician Global Assessment (sPGA) of clear or almost clear (sPGA of 0 or 1) at Week 16. This study is also powered to show a benefit in PASI 90 response at Week 44 between the subjects re-randomized to continue on adalimumab vs. subjects randomized to risankizumab at Week 16.

Based on the assumption that the Week 44 PASI 90 rate will be approximate 40% for adalimumab and 70% for risankizumab for the subjects who are re-randomized at Week 16, a total of 120 subjects will result in > 90% power for the primary efficacy analysis in Part B using a type-I error rate at 5%. See Table 1 sample size calculations for different scenarios. Assuming for those subjects originally randomized to adalimumab the response rate at Week 16 for PASI 90 and PASI 50 are 45% and 85%, respectively, then this leaves approximately 40% of subjects expected to fall in the more than or equal

to PASI 50 and less than PASI 90 range and thus be eligible for re-randomization. This requires that 300 (40% of 300 = 120) subjects be randomized to adalimumab at randomization.

Based on the outcome from Trials 1311.1 and 1311.2, the PASI 90 response rate at Week 16 is assumed to be at least 65% in the risankizumab arm. For the primary analysis comparing risankizumab to adalimumab, sample sizes of 300 per arm will allow for > 90% power assuming 70% and 50% PASI 90 response rates for risankizumab and adalimumab, respectively. See [Table 2](#) for more sample size calculations.

Table 1. Sample Sizes for 90% Power for Testing Against Adalimumab Using PASI 90 at Re-Randomization

Risankizumab	Adalimumab	Delta	Re-Randomization Ratio Risankizumab:Adalimumab = Total N
65%	40%	25%	82:82 = 164
70%	45%	25%	80:80 = 160
70%	40%	30%	56:56 = 112
75%	45%	30%	54:54 = 108
80%	50%	30%	51:51 = 102

Table 2. Sample Sizes for 90% Power for Testing Against Adalimumab Using PASI 90

Risankizumab	Adalimumab	Delta	Randomization Ratio Risankizumab:Adalimumab = Total N
65%	50%	15%	226:226 = 452
70%	55%	15%	217:217 = 434
70%	50%	20%	124:124 = 248
75%	55%	20%	118:118 = 236
70%	45%	25%	80:80 = 160
75%	50%	25%	77:77 = 154

Based on the outcome from Trials 1311.1 and 1311.2, the achievement of sPGA clear or almost clear rate at Week 16 is assumed to be at least 85% in the risankizumab arm.

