11.2 Analysis of Adverse Events

11.2.1 Treatment-Emergent Adverse Events

Treatment-emergent adverse events (TEAEs) are defined as any event with an onset that is after the first dose of study drug and with an onset date within 105 days after the last dose of study drug in the analysis period, or prior to the first dose in the subsequent period for subjects who entered in to the subsequent period. Events where the onset date is the

same as the study drug start date are assumed to be treatment-emergent, unless the adverse event start time is prior to the study drug start time. If an incomplete onset date is collected for an adverse event, the event will be assumed to be treatment-emergent unless there is other evidence that confirms that the event is not treatment-emergent (e.g., the event end date is prior to the study drug start date).

Treatment-emergent adverse events (TEAE) for each safety population are defined as follows:

TEAEs of Safety_A:

For subjects who do not enter Part B, TEAEs are defined as any event with an onset after the first dose of study drug and no more than 105 days after the last dose of study drug.

For subjects who enter Part B, TEAEs are defined as any event with an onset after the first dose of study drug in Part A and before the first dose of study drug in Part B.

TEAEs of Safety_B_RR, Safety_B_R, Safety_B_NR:

TEAEs are defined as any event with an onset after the first dose of study drug in Part B and no more than 105 days after the last dose of study drug in the study.

TEAE of ALL_RZB:

TEAEs are defined as any event with an onset after the first dose of risankizumab and no more than 105 days after the last dose of risankizumab in the study.

The number and percent of subjects experiencing treatment-emergent TEAEs will be tabulated using the Medical Dictionary for Drug Regulatory Activities (MedDRA®) system organ class and preferred term.

Summary tables will be presented as follows:

1. Adverse Event Overview

The number and percentage of subjects experiencing treatment-emergent adverse events will be summarized for the following adverse event categories:

- Any AE
- Any AE that was assessed as related to study drug by the investigator
- Any severe AE
- Any serious AE (SAE)
- Any serious AE that was assessed as related to study drug by the investigator
- Any AE leading to discontinuation of study drug
- Any AE leading to death
- Any deaths
- Areas of Safety Interest

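### SAP 11.1 plans between-arm safety tests that the protocol says are not planned, and shows AE P values only up to 0.100, with no effect estimate or interval

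*SAP*

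**What the plan says.** **Protocol.** Section 5.3 opens: "Safety will be assessed descriptively based on". Section 7.3.4 says that safety analyses are in general descriptive and follow the standards of the sponsor responsible for the statistics. It adds: "No hypothesis testing is planned". Further detail is left to the statistical analysis plan.

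**SAP.** Section 11.1 says: "Comparison between risankizumab group and adalimumab group will be performed in the Safety Population in Safety_A and Safety_B_RR populations". Continuous safety variables get a one-way ANOVA, and "categorical variables will be analyzed using Fisher's exact test". For AEs, "only P values ≤ 0.100 when rounded to three digits will be presented". In section 11.2.1, "The number and percent of subjects experiencing treatment-emergent TEAEs will be tabulated", by system organ class (SOC) and preferred term (PT). The same section plans an AE overview that includes the Areas of Safety Interest, by-subject listings, and event rates per 100 patient-years. Section 11.2.3 repeats the AE overview and the SOC/PT analysis by weight and prior TNF exposure.

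Section 14.1 lists the changes from the protocol. Its only safety item is the pre-specification of Areas of Safety Interest.

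**The concern.** The protocol rules out safety hypothesis tests. The SAP introduces them across AEs and the other safety variables without recording a departure. For AEs it then filters what is shown by the size of the P value.

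This makes a weak readout in two ways. A P value that is printed has been selected from many rows and carries no multiplicity adjustment; the hierarchy in SAP 10.4 covers efficacy only. A P value that is not printed leaves an empty cell, which a reader can take to mean no difference, although it may only mean few events. No planned risk difference or interval tells the two apart.

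Safety against adalimumab is part of the trial's main objective (protocol 2.2, SAP 4.1), so the form of the comparison matters. It matters most for Areas of Safety Interest such as adjudicated cardiovascular events, tuberculosis and malignancy, which are likely to be infrequent.

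**Working it through.** **Inputs.** Part A has 300 per arm: "sample sizes of 300 per arm will allow for > 90% power assuming 70% and 50% PASI 90 response rates" (SAP 4.3). The re-randomized set has 120 planned, hence 120 / 2 = 60 per arm at 1:1 (SAP 4.2 and 4.3). The display rule is P at most 0.100 after rounding to three digits (SAP 11.1). The SAP does not state sidedness for safety tests, so two-sided is assumed. The documents give no AE rates, so all rates below are assumptions.

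**Step 1: the plan's own figures.** The only stated power figures are for efficacy. For 70% v 50%, two-sided 0.05 and 90% power:

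n = [1.960 × √(2 × 0.6 × 0.4) + 1.282 × √(0.7 × 0.3 + 0.5 × 0.5)]² / 0.20² = (1.358 + 0.869)² / 0.04 ≈ 124 per arm.

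This matches the stated 124. All 14 distinct rate pairs in SAP Tables 1 to 3 reproduce within one patient per arm. The documents state no figure for detecting an AE imbalance.

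**Step 2: chance that a P value is shown.** For counts a and b with n per arm, the Fisher P value is the sum of the hypergeometric probabilities no larger than that of the observed table. The chance of display is the sum over all (a, b) of Bin(a; n, p₁) × Bin(b; n, p₂), counting only tables whose rounded P is at most 0.100. Exact enumeration gives:

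| Assumed true rates | n per arm | P value shown |
|---|---|---|
| 1% v 2% | 300 | 15% |
| 2% v 4% | 300 | 33% |
| 1% v 3% | 300 | 43% |
| 1% v 4% | 300 | 70% |
| 5% v 10% | 300 | 71% |
| 10% v 20% | 300 | 96% |
| 2% v 5% | 60 | 7% |
| 5% v 10% | 60 | 17% |
| 10% v 20% | 60 | 37% |
| 5% v 15% | 60 | 48% |
| 5% v 20% | 60 | 76% |
| 10% v 30% | 60 | 83% |

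**Step 3: no true difference.** At 300 per arm a P value is still shown in about 3% of rows at a 1% event rate, and in about 8% at rates of 10% to 50%.

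**Step 4: where the cut falls.** At 300 per arm, 2 v 8 events gives P = 0.106 (blank) and 2 v 9 gives P = 0.063 (shown). At 60 per arm, 0 v 4 gives P = 0.119 (blank) and 0 v 5 gives P = 0.057 (shown). One event decides whether the cell is filled.

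**Step 5: what an interval adds.** Take 8/300 v 3/300, for which P = 0.22 and the cell is blank. The Wilson limits are 1.36% to 5.17% around 2.67%, and 0.34% to 2.90% around 1.00%. The Newcombe limits for the difference of 1.67 points are:

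- lower: 1.67 − √[(2.67 − 1.36)² + (2.90 − 1.00)²] ≈ −0.6 points
- upper: 1.67 + √[(5.17 − 2.67)² + (1.00 − 0.34)²] ≈ +4.3 points

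For 4/60 v 0/60 (P = 0.119, blank) the same method gives −0.6 to +15.9 points. Both intervals include zero, but they show how large an excess the data leave open.

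**The case against.** A reader might infer that the display rule hides safety imbalances. The documents do not support that. The rule applies to P values only. With 8 v 3 events the table still prints 8 (2.7%) and 3 (1.0%). Deaths, serious AEs, AEs leading to discontinuation of study drug and Areas of Safety Interest are also listed by subject.

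A reader might also infer that most real differences would have a blank P value. That depends on rates the documents do not give. It is so for doublings from 1% or 2% in Part A, and for moderate differences at 60 per arm. It is not so for 5% v 10% or 10% v 20% at 300 per arm, or for 5% v 20% at 60 per arm.

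The protocol conflict can be read mildly. Section 7.3.4 describes safety analyses as descriptive only in general and defers detail to the SAP. The SAP attaches no alpha, hypothesis or decision rule to these P values, so they act as nominal flags. Protocol 5.1 states that no primary or secondary endpoint is a safety issue, so no confirmatory conclusion is affected. This limits the weight of the point but does not remove it. The no-testing sentence carries no qualifier of its own, and the SAP neither labels the P values nominal nor records the change. By contrast, SAP 11.3.2 does explain its departure from the protocol's laboratory grading scale.

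Two further objections stand and shape the fix. Unadjusted intervals over many rows raise the same multiplicity question, so they need a label. Removing only the AE P values would leave the ANOVA and the other Fisher comparisons in conflict with the protocol.

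**Conclusion.** The point holds as an unrecorded mismatch between SAP 11.1 and protocol 7.3.4, together with a weak way of presenting AE comparisons. Imbalances remain visible as counts and percentages. What is missing is a between-arm estimate with its uncertainty, and what is shown in its place is selected by its own size.

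Under the assumed rates the chance that a P value appears runs from 15% (1% v 2%) to 96% (10% v 20%) at 300 per arm, and from 7% (2% v 5%) to 83% (10% v 30%) at 60 per arm. A blank therefore cannot be read as absence of a difference, least of all for rare events or in the re-randomized set. These figures rest on two-sided Fisher tests, independent binomial counts, full planned arm sizes and illustrative rates. The textual mismatch rests on none of these assumptions. No efficacy conclusion is at risk.

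**What to change.** In SAP 11.1, remove the AE P values and the 0.100 display rule. For each AE overview row and each Area of Safety Interest, in Safety_A and Safety_B_RR, print the risk difference with a two-sided 95% confidence interval (for example Newcombe), labelled descriptive and not adjusted for multiplicity. Keep the SOC and PT tables descriptive.

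Make the ANOVA and the other Fisher safety comparisons in the same section descriptive too. If any P values are kept, label them nominal and unadjusted, show them for every row whatever their size, and list the departure from protocol 7.3.4 in SAP 14.1.

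The cost is SAP wording, one extra table column and the loss of a familiar P value column. Data collection, sample size and trial conduct do not change.

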6.0 Analysis Conventions

Definition of Baseline:

The last non-missing measure collected on or before the date of the first dose of study drug injection will be used as Baseline for summary of demographics and disease characteristics, efficacy analyses, and safety analyses in each period, with the exception that:

- The last evaluation on or prior to the first dose date of risankizumab will be used for the safety analyses for ALL_RZB populations.
- For all vital sign assessments, only assessments prior to first dose time will be considered, since vital signs are to be assessed both pre- and post-dose in some visits.

For subjects who are randomized but do not take any study drug during the study, the last non-missing measurement collected on or before the date of randomization will be used as Baseline.

Definition of Final Observation (Applicable to Safety Analyses):

Final observation for the Part A is defined as:

- The last non-missing observation collected within 105 days following the last dose of study drug in Part A for subjects who were not dosed in Part B.
- The last non-missing observation collected on or before the first dose date of study drug on or after Week 16 and within 105 days following the last dose of study drug in Part A for subjects who were dosed in Part B. For vital sign assessments, only assessments prior to the first dose of study drug injection in Part B will be included in the analysis for Part A.

Final observation in Part B and in the entire study is defined as the last non-missing observation collected within 105 days after the last dose of study drug.

Definition of Rx Days (Days Relative to the Date of First Dose of Study Drug)

Rx days are calculated for each time point relative to the date of first dose of study drug. They are defined as the number of days between the day of the first dose of study drug and the specific time point. Rx days are negative values when the time point of interest is prior to the first study drug dose day. Rx days are positive values when the time point of interest is on or after the first study drug dose day. The day of the first dose of study drug is defined as Rx Day 1, while the day prior to the first study drug dose is defined as Rx Day -1 (there is no Rx Day 0).

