10.1.2 Analyses of Continuous Variables

For continuous variables, the model based mean and standard error will be presented. The Baseline and visit means will also be presented for each treatment group for subjects who have both Baseline and post Baseline visit values. The treatment groups will be compared using ANCOVA with treatment group, Baseline value, and stratification factors in the model.

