11.3.2 Statistical Methods

Analysis of Quantitative Laboratory Parameters (Hematology and Chemistry)

Though the protocol indicates utilizing the Rheumatology Common Toxicity Criteria (RCTC) scale for grading laboratory values, given that the National Cancer Institute Common Toxicity Criteria for Adverse Events (NCI CTCAE) scale includes a more comprehensive list of laboratory values; the lab analyses based on the NCI CTCAE scale will be presented. Changes from Baseline to each scheduled visit and to the final value in continuous laboratory parameters will be summarized with the mean, standard deviation and median. The Baseline and visit/final value means will also be presented for subjects who have both the Baseline and visit/final values (see Section 6.0 for the definition of Baseline and final values).

If there are multiple post-baseline measurements on the same day, average value will be used.

Shift Tables

Shift tables for changes from Baseline according to the normal range will be provided for each hematology and clinical chemistry parameter. Shifts from Baseline to the following endpoints will be considered: minimum value, maximum value and final value.

Categories of "low or normal" and "high or normal" will be included at Baseline in addition to the categories of "low," "normal," "high" and "missing."

If there are multiple post-baseline measurements on the same day, the last value will be used.

Potentially Clinically Important Laboratory Values

Frequencies and percentages of subjects with post Baseline lab values meeting the following criteria will be summarized. Of note, a post baseline value must be more extreme than the baseline value to be considered a potentially clinically important finding.

Table 23. Criteria for Potentially Clinically Important Chemistry Values

Chemistry Variables	Units	Definition of Potentially Clinically Important Current (Version 4) NCI CTCAE Grade 3 or Greater	
		Very Low	Very High
TBL	mcmol/L		> 3.0 × ULN
SGOT/AST	U/L		> 5.0 × ULN
SGPT/ALT	U/L		> 5.0 × ULN
Albumin	g/L	< 20	
Glucose	mmol/L	< 2.2	> 13.9
Triglycerides	mmol/L		> 5.7
Creatinine	mcmol/L		> 3.0 × ULN
Sodium	mmol/L	< 130	> 155
Potassium	mmol/L	< 3.0	> 6.0
Calcium	mmol/L	< 1.75	> 3.1
CPK	U/L		> 5.0 × ULN
Total Cholesterol	mmol/L		> 10.34
GGT			> 5.0 × ULN
ALP			> 5.0 × ULN

Note: A post baseline value must be more extreme than the baseline value to be considered a potentially clinically important finding.

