11.4.2 Statistical Methods

Changes from Baseline to each visit and to the final value in vital sign parameters will be summarized with the mean, standard deviation and median. The Baseline and final value means will also be presented for subjects who have both the Baseline and final values (see Section 6.0 for the definition of Baseline and final values).

For baseline, if there are multiple measurements on the same day, the last measurement prior to the first dose of study drug will be used as the Baseline vital sign value. If there are multiple post-baseline measurements on the same day, average value will be used.

For systolic blood pressure, diastolic blood pressure and pulse, a listing of all subjects with any vital sign value meeting criteria for potentially clinically important values will be

provided. For each of these subjects, the whole course of the respective parameter will be listed. The number and percentage of subjects who have at least one value meeting criteria for potentially clinically important values will be provided for each selected vital sign parameter.

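### Between-arm comparisons of laboratory and vital-sign change omit baseline as a covariate and so give up some precision for no saving

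*SAP*

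**What the plan says.** SAP 11.1 plans between-arm safety comparisons: "Comparison between risankizumab group and adalimumab group will be performed in the Safety Population in Safety_A and Safety_B_RR populations". The method is given in the next sentence: "Continuous variables will be analyzed using one-way ANOVA". A one-way ANOVA has treatment as its only factor, and no covariate is named.

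The outcome scale comes from the later sections. SAP 11.3.2, laboratory: "Changes from Baseline to each scheduled visit and to the final value in continuous laboratory parameters will be summarized". SAP 11.4.2, vital signs: "Changes from Baseline to each visit and to the final value in vital sign parameters will be summarized". In both, the listed statistics are the mean, standard deviation and median.

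A baseline exists for these variables. SAP 6.0: "The last non-missing measure collected on or before the date of the first dose of study drug injection will be used as Baseline". That rule covers safety as well as efficacy analyses, and SAP Tables 9 and 10 define an Entry-of-B window for laboratory, ECG and vital-sign data in Safety_B_RR.

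For continuous efficacy variables, SAP 10.1.2 uses a fuller model: "The treatment groups will be compared using ANCOVA with treatment group, Baseline value, and stratification factors in the model".

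Protocol 7.3.4 describes the safety analyses as generally descriptive and plans no hypothesis tests on them.

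**The concern.** The same SAP uses two models for the same kind of quantity, a continuous change from baseline compared between randomised arms. Efficacy gets baseline and strata in the model; safety gets treatment alone. No reason is given for the simpler safety model.

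Subtracting baseline fixes its coefficient at 1. If the regression slope of follow-up on baseline is below 1, as it is with equal variances and rho below 1, subtraction over-corrects and leaves avoidable baseline noise in the treatment difference. What is at stake is the precision of the mean laboratory and vital-sign differences between risankizumab and adalimumab. Safety against adalimumab is a main objective of the trial (Protocol 2.2, SAP 4.1).

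**Working it through.** **Inputs.** The documents give no standard deviation, correlation, effect size or power for any laboratory or vital-sign comparison, so there is no planned figure to reproduce. From SAP 4.3: 300 patients per arm in Part A and 120 re-randomised in Part B, that is 60 per arm at 1:1. The correlation rho is assumed, over 0.3 to 0.95. SAP 11.1 does not name the dependent variable of the ANOVA; following SAP 11.3.2 and 11.4.2, it is taken to be the change from baseline.

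**Formulas.** Let s0 and s1 be the baseline and follow-up standard deviations. Per-patient variance of the outcome after each adjustment:

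- ANOVA on change: s0² + s1² − 2·rho·s0·s1
- ANCOVA: s1²·(1 − rho²)

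The first minus the second is s0² − 2·rho·s0·s1 + rho²·s1² = (s0 − rho·s1)², which is never negative. Apart from degrees of freedom, ANCOVA therefore cannot do worse in this model. The full ANCOVA (baseline and two binary strata) uses three more degrees of freedom: 598 becomes 595 in Part A and 118 becomes 115 in Part B, which is negligible.

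With s0 = s1 = s, the two variances are 2s²(1 − rho) and s²(1 − rho²), so

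ratio = (1 − rho)(1 + rho) / [2(1 − rho)] = (1 + rho)/2.

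The SE ratio is its square root.

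| rho (assumed) | Variance ratio | SE ratio | SE reduction |
|---|---|---|---|
| 0.3 | 0.65 | 0.806 | 19% |
| 0.5 | 0.75 | 0.866 | 13% |
| 0.7 | 0.85 | 0.922 | 8% |
| 0.8 | 0.90 | 0.949 | 5% |
| 0.9 | 0.95 | 0.975 | 2.5% |
| 0.95 | 0.975 | 0.987 | 1.3% |

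**In units of s, at rho = 0.5.** The SE of the arm difference is √[2(1 − rho)]·√(2/n) for change and √(1 − rho²)·√(2/n) for ANCOVA.

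- n = 300 per arm: 0.0816 against 0.0707
- n = 60 per arm: 0.1826 against 0.1581

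The ratio is 0.866 in both, because n cancels.

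**Simulation check** (4,000 runs per setting, normal data, no treatment effect). Empirical variance ratios for rho 0.5, 0.7 and 0.9 were 0.754, 0.843 and 0.960 at 300 per arm, and 0.746, 0.869 and 0.958 at 60 per arm. Theory gives 0.75, 0.85 and 0.95.

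The table credits baseline only. Any gain from the two strata would be additional and cannot be sized from the documents.

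**The case against.** The strongest reply is that this is a preference, not an error. The protocol makes safety descriptive, no decision rule rests on a laboratory or vital-sign mean, and clinically important changes are picked up elsewhere in SAP 11: shift tables, potentially clinically important values, grade 3 or higher listings, liver-test and Hy's Law listings, and QTc categories. None of these depends on the ANOVA. All of that stands, and it limits the consequence. It does not remove the gain, because SAP 11.1 still plans the comparison.

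Four stronger readings are tempting, and the documents do not support them.

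- **That baseline is ignored.** It is not. The outcomes are changes; only the covariate is absent.
- **That the ANOVA is biased or produces excess false positives.** Under randomisation it is unbiased, regression to the mean acts on both arms alike in expectation, and its standard error already allows for chance imbalance. Given an observed imbalance of k standard errors, the change comparison does shift by k·√[(1 − rho)/2] of its own standard errors (at rho = 0.5 and k = 2, by 1). ANCOVA removes that shift, but averaged over randomisations this is lost efficiency, not inflated error. The relative loss is no greater at 60 per arm than at 300.
- **That planned confidence intervals are too wide.** SAP 11 specifies no interval for these variables.
- **That a fixed number of patients is wasted.** No sample size is based on these variables, and the size of the gain depends on a rho that the documents do not give.

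A related matter lies in the same section: SAP 11.1 plans between-arm safety comparisons and reports adverse-event p-values up to 0.100, although Protocol 7.3.4 plans no testing, and SAP 14.1 does not list this as a change. Changing the model does not settle that, which is why the adjusted estimate should be labelled descriptive.

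**Conclusion.** The point holds as an optional efficiency improvement. The planned one-way ANOVA on change is valid but less precise than the ANCOVA the SAP already specifies for efficacy. The SE reduction runs from about 19% at rho 0.3 to about 1% at rho 0.95, and is about 13% or less once rho reaches 0.5. For very stable parameters it is negligible.

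The figures assume that the ANOVA is applied to change, that baseline and follow-up variances are equal, and the stated values of rho. The direction does not need equal variances. No alpha, power, sample size or efficacy conclusion changes.

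**What to change.** In SAP 11.1, for change from baseline in laboratory and vital-sign variables, replace the one-way ANOVA with an ANCOVA containing treatment, the baseline value, weight stratum (≤ 100 kg, > 100 kg) and prior TNF-antagonist exposure (0, ≥ 1). For Safety_B_RR, name the Entry-of-B value as the baseline covariate. Report the adjusted treatment difference with a 95% CI, labelled descriptive, in line with Protocol 7.3.4.

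The cost is about one sentence in the SAP. No new data are needed, and since the model is that of SAP 10.1.2 ("compared using ANCOVA with treatment group, Baseline value, and stratification factors in the model"), its programming can largely be reused. The change should be made before database lock.
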